4.10 Scales & Forms

We will offer clinical interviews and study forms in Spanish. All scales will explore the last 7 days, except M.I.N.I (lifetime), TSRQ (study duration).

- **(M.I.N.I.)** - The M.I.N.I. is a brief structured diagnostic interview, developed jointly by psychiatrists and clinicians in the United States and Europe, for DSM and ICD psychiatric disorders. With an administration time of approximately 15 minutes, it is designed to meet the need for a short but accurate structured psychiatric interview for clinical trials. According to researchers in the Division of Clinical and Treatment Research at the National Institute of Mental Health (NIMH), the M.I.N.I. is a fully validated and more time-efficient alternative to the Structured Clinical Interview for DSM Disorders (SCID) (Sheehan et al., 1998). Validated in Spanish (Ferrando L. et. al, 1998).
- **Systematic Assessment for the Treatment of Emergent Events (SAFTEE-SI)** - The SAFTEE is a commonly used instrument originally developed by NIMH and adapted into a self-report instrument. The version of the scale we plan to use is the same

Transcranial Near Infrared Laser Therapy in Subjects with Major Depressive Disorder: A Laser Dosing Study.

used by the NIMH-sponsored CO-MED multicenter trial, and systematically examines all potential treatment-emergent side effects and discusses specific adverse symptoms, including suicidal thoughts and behaviors, and self-injurious behavior.

- **Hamilton Depression Rating Scale - 17 items (HAM-D-17)**; Hamilton, 1960

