 - The doctor completes this instrument based on his or her assessment of the patient's depressive symptoms, using a structured interview and defined anchor items. The goal of the HAM-D is to quantify the degree of depression in patients who already have a diagnosis of major depression. Questions focus on neurovegetative and other depressive symptoms experienced in the past 7 days. There are several different versions of the HAM-D; they differ only in the number of questions included. The standard form generally used in research studies is the 17-item Hamilton D (HAM-D-17). Responses to the questions are scored on a scale of 0-4 or 0-2, with higher scores indicating more severe pathology. Scores on the HAM-D-17 generally fall into the following ranges: a) not depressed = 0-7; b) mildly depressed = 8-13; c) moderately depressed = 14-18; d) severely depressed = 19-22; e) very severely depressed = 23 or more. Validated in Spanish by Ramos-Brieva (1986).
- **Quick Inventory of Depressive Symptomatology: Clinician-Rated Scale (QIDS-C)** - This is a brief (16-item) clinician-rated inventory of core depressive symptoms such as sleep, depressed mood, appetite, concentration, suicidal ideation, interest, energy, psychomotor retardation, or agitation. Validated in Spanish by Planas et al. (2014).
- **Clinical Global Impressions: Severity and Improvement (CGI-S, CGI-I)** - The clinician scores these two instruments from 1 to 7 based on the assessment of the subject's overall clinical status. Measured based on history and scores on other instruments: (a) depressive severity (CGI-S) and (b) clinical improvement (CGI-I). Validated in Spanish by García-Portilla (2011).
- **Anxiety Symptom Questionnaire (ASQ)** - This is a 17-item self-report questionnaire, used in Spanish, that measures the frequency and intensity of 17 anxiety symptoms, including nervousness, worry, irritability, trouble relaxing, insomnia, lack of energy, difficulty concentrating, somatic symptoms, and impaired functioning due to anxiety.

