- **Symptoms of Depression Questionnaire (SDQ)** - This is a comprehensive measure of depression that includes assessment of symptoms on the anxiety-depression spectrum. It assesses irritability, anger outbursts, and anxiety symptoms along with symptoms commonly considered to be symptoms of depression. Factor structure analysis of the SDQ identified 5 subscales, including one on the anxiety-depression spectrum, with adequate internal consistency and concurrent validity in Spanish (Pedrelli et al., 2014).
- **Columbia Suicide Severity Rating Scale (C-SSRS)** For suicidal ideation and behavior: an FDA-endorsed instrument for clinical trials. This instrument systematically tracks suicidal ideation and behavior (e.g., suicide attempts, desire to die, suicidal thoughts, plan and intent) (Posner et al. 2007) Validated in Spanish by Al-Halabí et al.(2016).
- **Adverse Event Form**- The adverse event form captures any adverse events (serious or otherwise) specifically related to the application of TLT. This form will help determine if the side effects of TLT are too great for a participant to continue in the study.
- **Concomitant Medication Form** - This form will be completed at each TLT study visit, including the screening visit, as a safety monitoring tool.

Transcranial Near Infrared Laser Therapy in Subjects with Major Depressive Disorder: A Laser Dosing Study.

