4.20 Summary of Risks and Benefits

4.20.1 Potential Adverse Events

Risks to the subject may include, but are not limited to, the following:

The EXPi device emits light with a wavelength longer than the human eye can see. Personnel will be trained in basic safety procedures related to the use of the device. Personnel administering the NIR-TLT will be careful not to operate the EXPi device unless it is in direct contact with the subject's skin. Both the subject receiving the NIR-TLT and the study doctor present in the NIR-TLT room will wear eye protection in the form of goggles or pads. The goggles provided with the EXPi device are in direct contact with the area surrounding the subject's eye. Since they are reusable, they should not be shared between subjects. The eye pads are disposable and should be discarded after use. The eye pads have an adhesive to adhere to the subject's eyelids, so there is a possibility of an allergic reaction.

EXPi device failure resulting in cessation of investigational therapy may cause:

1. No adverse events to our knowledge
2. Unforeseeable adverse events

Delivery of infrared energy to an inappropriate site, such as directly over the open eye, is not recommended and could pose a risk to the subject.

The application of the EXPi device may cause a slight thermal sensation of heat during use. The skin temperature is well below the thermal damage level.

Based on human clinical trial experience to date, each adverse event listed below has been reported with TLT:

1. Erythema at the application site
2. Pain at the application site
3. Discomfort at the application site
4. Heat at the application site
5. Reaction at the application site
6. Headache

Additional potential side effects of NIR-TLT, documented in previous trials, include:

- See bright colors, abnormal taste
- Feeling "out-of-body" experiences
- Insomnia, restless sleep, erratic sleep, early morning awakening.
- Vivid dreams
- Irritability
- Difficulty finding words
- Abdominal distention

Other potential risks are described below:

Transcranial Near Infrared Laser Therapy in Subjects with Major Depressive Disorder: A Laser Dosing Study.

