5.5 Efficacy and Safety Analysis for the Aims

It will be carried out as follows:

A. Antidepressant effect of NIR-TLT doses:

To compare the antidepressant effects of NIR-TLT doses, mean changes in HAM-D 17 scores (for evaluation of the Primary Assessment Criteria) and QIDS-C and CGI-S (for evaluation of the Secondary Assessment Criteria), will be performed for each dose at 3 time points (visit 1, visit 9 and visit 18) will be compared using a repeated measures ANCOVA. A significant ANCOVA interaction in mean score changes between groups will be taken as indicating that the groups have different antidepressant efficacy. If significant ANCOVA interactions are found, paired samples t-tests will be used to explore differences between scores/groups.

Both the full analysis and the analysis by intention will be performed to analyze the severity of depression at the endpoint. Patient attrition and dropout will be analyzed. The possible

Transcranial Near Infrared Laser Therapy in Subjects with Major Depressive Disorder: A Laser Dosing Study.

differences between treatment groups in dropouts will be examined with Fisher's exact test.

B. Brain electrophysiological effect of NIR-TLT doses:

To compare the effects of NIR-TLT doses on brain electrophysiology, changes in EEG spectral power in all spectral bands for each dose at 3 time points (visit 1, visit 9, and visit 18) will be compared using a repeated measures ANCOVA. A significant ANCOVA interaction in mean score changes between groups will be taken as indicating that the groups have different effects. If significant ANCOVA interactions are found, paired samples t-tests will be used to explore differences between groups.

C. Safety and tolerability of NIR-TLT doses:

To compare the safety and tolerability of NIR-TLT doses, mean changes iSAFTEE-SI scores at 3 time points (visit 1, visit 9, and visit 18) will be compared using a repeated measures ANOVA. A significant ANOVA interaction in mean score changes between groups will be taken as indicating that the NIR-TLT doses have different tolerability. If significant ANOVA interactions are found, paired samples t-tests will be used to explore differences between groups.

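### Section 5.5 C reads a significant group-by-time interaction in mean SAFTEE-SI change as different tolerability, although relief of depression alone can produce that interaction

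*Protocol*

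**What the plan says.** Protocol Section 5.5 C analyses SAFTEE-SI scores at visits 1, 9 and 18 by repeated measures ANOVA and fixes the inference: "A significant ANOVA interaction in mean score changes between groups will be taken as indicating that the NIR-TLT doses have different tolerability". Follow-up t-tests are planned if the interaction is significant. Nothing is said about the direction of a difference, about leaving out depressive items, or about counting only symptoms that appeared or worsened after visit 1.

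Section 4.9.2 has the safety scales completed before the laser at each treatment visit, so the visit 1 score precedes all treatment. Section 4.10 says that the form "systematically examines all potential treatment-emergent side effects", "including suicidal thoughts and behaviors, and self-injurious behavior".

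The same Section 5.5 C then adds a comparison of the frequency and severity of side effects and adverse events between doses by Fisher's exact test, with relatedness and corrective actions reported. Section 5.6 tabulates adverse events by group. Hypothesis 2 (Sections 4.1 and 5.2) names SAFTEE-SI and serious adverse events as the basis for judging safety and tolerability.

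**The concern.** A change score measures side effects only if the starting score is free of the disease. Here it probably is not. Participants enter with QIDS-C of at least 12 and CGI-S of at least 4. A fall in SAFTEE-SI after visit 1 is a loss of symptoms that were present before treatment; a rise may be a side effect. The mean change nets the two.

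The stated rule then has two weaknesses. First, if one arm relieves depression more than sham, its mean SAFTEE-SI score can fall further, and a significant interaction is to be called different tolerability even when side effects are the same in every arm. Secondly, if an effective arm also causes side effects, relief and harm pull the mean score in opposite directions. Both arise when a dose works, which is the result the trial is designed to find.

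**Working it through.** **Overlap, as far as the Protocol documents it**

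- Suicidal thoughts: explicit SAFTEE-SI content (Section 4.10). The QIDS-C entry in the same section describes that scale as covering "core depressive symptoms such as sleep, depressed mood, appetite, concentration, suicidal ideation, interest, energy", so suicidal ideation and sleep are depressive symptoms on the Protocol's own account.
- Sleep: Section 4.20.1 lists "Insomnia, restless sleep, erratic sleep, early morning awakening" among documented effects of the laser. A form meant to cover all potential side effects should include them. This is an inference.
- Irritability: listed as a laser effect in Section 4.20.1 and also part of the SDQ, a depression measure: "It assesses irritability, anger outbursts, and anxiety symptoms along with symptoms commonly considered to be symptoms of depression". Its presence on SAFTEE-SI is again an inference.

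Some overlap is therefore documented. Its share of the total score is not.

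**Inputs from Section 5.3**

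Difference 6.4, SD 7.091, alpha 0.05, power 90%, loss 20%, 28 per group, 112 in total. Standardised effect: 6.4 / 7.091 = 0.90.

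The plan's own figure, one-sided: n = 2 × (1.645 + 1.282)² / 0.9026² = 21.03, rounded up to 22; 22 / 0.80 = 27.5, rounded up to 28; 4 × 28 = 112. This reproduces the plan (the two-sided version gives 26, then 33, then 132). It matters here only because it supplies the two group sizes used below: 28 randomised and 22 after losses. The Protocol gives no figure for the SAFTEE-SI test itself.

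**Assumption**

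Let w be the share of the 0.90 SD benefit that appears as a fall in SAFTEE-SI, in SDs of SAFTEE-SI change. The Protocol does not give w; 0.3, 0.5 and 0.7 are illustrative. All three active arms are equally effective, and side effects do not differ between arms. The SAFTEE-SI shift against sham is e = w × 0.9026: 0.27, 0.45 or 0.63 SD.

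**Check 1: change at one visit, four-arm F test**

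λ = n × [3(e/4)² + (3e/4)²] = 0.75 × n × e², with 3 and 4n − 4 degrees of freedom. At n = 22 and w = 0.5: 0.75 × 22 × 0.4513² = 3.36.

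**Check 2: the planned interaction**

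Simulation of a group-by-time interaction over three visits (6 degrees of freedom), 4,000 trials per cell, between-visit correlation 0.5 (so the SD of change is √(2 × 0.5) = 1), half the shift at visit 9 and all of it at visit 18. The Monte Carlo standard error is at most √(0.5 × 0.5 / 4000) = 0.008.

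| w | e (SD) | One visit, n = 22 | One visit, n = 28 | Interaction, n = 22 | Interaction, n = 28 |
|---|---|---|---|---|---|
| 0 | 0 | 0.05 | 0.05 | 0.05 | 0.06 |
| 0.3 | 0.27 | 0.13 | 0.15 | 0.11 | 0.12 |
| 0.5 | 0.45 | 0.29 | 0.37 | 0.23 | 0.28 |
| 0.7 | 0.63 | 0.54 | 0.66 | 0.42 | 0.53 |

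The interaction columns match the planned test and are the ones to use; the one-visit shortcut runs higher.

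**Check 3: offsetting within the mean score**

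Add a real side-effect burden of 0.5 SD (assumed) in all active arms, n = 28, interaction test. The net shift is 0.5 − 0.9026w.

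| w | Net shift (SD) | Probability of a significant interaction |
|---|---|---|
| 0 | 0.50 | 0.33 |
| 0.3 | 0.23 | 0.09 |
| 0.55 | 0.00 | 0.05 |

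Cancellation is complete at w = 0.5 / 0.9026 = 0.55.

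**The case against.** **Harm has another route to detection.** Section 5.5 C itself adds the Fisher comparison, and Section 5.6 the adverse event table. A reader might infer that the plan as a whole could hide side effects; the Protocol does not support that. This stands, and it limits the masking argument to the mean score. It does not rescue the rule: the Fisher comparison is an addition, so a significant interaction would still be declared different tolerability. Section 5.5 also does not say whether a side effect counted there must be new or worse than at visit 1.

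**The item list and scoring are not shown.** The form is described as covering treatment-emergent side effects, not every symptom, and only suicidal thoughts and self-injury are named as overlapping content. Participants with suicidal intent and plan are excluded, which trims the severe end of that content. The size of the bias therefore cannot be derived from the Protocol. Its direction needs only some overlap. A statistical analysis plan might define the score as a count of emergent symptoms, but that fits poorly with a rule that analyses a score at visit 1, before any treatment.

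**The percentages rest on assumption.** They require the antidepressant effect to pass into SAFTEE-SI in a fixed proportion, which no passage gives. This stands; they are illustrations over a range.

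**The rule says different, not worse.** Readers would see a larger fall in an active arm's means. True, but the rule still attaches the word tolerability to what may be efficacy. It is also only a significant interaction, not any group difference, that triggers the rule.

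**Conclusion.** The point holds in a limited form. The inference fixed in Section 5.5 C does not follow from the test: a significant interaction in mean SAFTEE-SI change can reflect relief of depression as well as side effects, and the rule does not separate them. With equal side effects in every arm, and 30% to 70% of the planned benefit carried into SAFTEE-SI in all three active arms, the test would be significant in roughly 11% to 42% of trials at 22 per arm, or 12% to 53% at 28, instead of 5%. These figures depend on the assumed overlap, a between-visit correlation of 0.5 and half the effect at visit 9. They are not expected error rates for this trial.

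Offsetting of side effects by relief is a property of the mean score alone. The wording should be changed before analysis. The data to be collected are not affected.

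**What to change.** In Section 5.5 C:

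1. Define the SAFTEE-SI tolerability outcome as items newly present or worse than at visit 1.
2. Report by arm the number of participants with at least one such item, and with each effect listed in Section 4.20.1 so far as the form contains it, with the difference from sham and its 95% confidence interval. Place this beside the Fisher comparison already planned.
3. Keep the mean score as a descriptive summary, read by direction.
4. Delete the sentence that takes a significant interaction as evidence of different tolerability.

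The cost is analysis wording and more item-level output. No new data are needed: the Section 8 table schedules SAFTEE-SI from screening to week 8. The change reduces the link with efficacy but does not remove it, since an effective arm may also have fewer items that worsen because the depression worsens. Direction should therefore still be considered when the item results are read.

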4.1 Study Aims

Primary Aim:

A. To evaluate and compare the effect(s) of each of the four doses of NIR-TLT on depressive symptomatology: antidepressant effect, in patients with major depressive disorder (MDD).

Hypothesis 1: Total HAM-D 17 scale scores will vary in a NIR-TLT dose-dependent manner, with BPW dose being more effective.

We also expect to be able to estimate the effect size of the antidepressant action as a function of the irradiance applied to the NIR-TLT skin, with the BPW dose being more effective.

Secondary Aims:

B. Compare safety and tolerability at each dose of NIR-TLT.

Hypothesis 2: The doses of NIR-TLT tested in this study will be safe and well tolerated by patients with MDD, as assessed by SAFTEE-SI and reports of serious adverse events. We do not anticipate dose-dependent differences in reported side effects.

C. To compare the effect(s) of each of the four doses of NIR-TLT on brain electrophysiology.

Exploratory Aim:

D. To describe the findings visualized in PET, related to the brain metabolism of the participants, before and at the end of the intervention under study.

4.2 Rationale for the use of the EXPi device:

Transcranial photobiomodulation (t-PBM) with near infrared (NIR) laser therapy has emerged as a possible antidepressant treatment in both animal models (Mohammed et al.2016; Salehpour 2016-2017; Xu et al.2017; Wu et al.2012), and in human studies (Cassano 2015- 2017; Caldieraro et al.2018) t-PBM. NIR appears to increase brain metabolism (by activating the cytochrome C oxidase in the mitochondria), to increase neuroplasticity and to modulate the

Near Infrared Transcranial Laser Therapy in Subjects with Major Depressive Disorder: A study of Dosing with Laser.

endogenous opioids, while decreasing inflammation and oxidative stress. (Chung et. al. 2012; Yu et. al. 1997; Oron et al. 2007, Mochizuki et al. 2002) t-PBM penetrates deep into the cerebral cortex, modulates cortical excitability, and improves cerebral perfusion and oxygenation. The safety of t-PBM has been studied in a sample of 1410 acute stroke patients, with no significant difference in adverse event rates between t-PBM and sham exposure. (Hacke et al. 2014; Lamp et al. 2007, Zivin et al. 2009) Uncontrolled studies suggest an antidepressant effect of t-PBM in subjects suffering from MDD (Cassano 2015-2017; Caldieraro et al. 2018).

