4.3 Dosing Rationale

The laser dose to be used in the present clinical trial is derived from previous clinical experience with the use of other versions of the medical device in studies conducted in patients with acute stroke, major depressive disorder and Alzheimer's disease in whom lasers have been administered with this device, which has provided guidance on safe and potentially effective doses in the study population. A summary of this information is presented in Table 1.

Laser devices have a potential risk of retinal injury when used incorrectly; this is mitigated by the use of protective eye equipment "goggles" and proper procedures to ensure eye safety (Barkana & Belkin, 2000).

No serious adverse events were found in our literature review (Caldieraro & Cassano, 2019). Two open-label studies using 1 and 6 sessions of t-PBM reported no treatment emergent side effects (Cassano et al., 2015; Schiffer et al., 2009).

The safety of a t-PBM session was evaluated in three large RCTs with a combined sample of 1410 stroke subjects (Hacke et al., 2014; Huisa et al., 2013; Lampl et al., 2007). No significant differences in the rate of adverse effects were observed between the group receiving NIR laser (808 nm; 5W, 700 mW / cm²) or sham.

A clinical trial with 16 sessions of t-PBM reported a higher number of mild side effects in the active treatment group, the most frequent being insomnia, "seeing bright colors," "an ashtray taste," and irritable mood (Cassano et al., 2018, p. 2). Other potential risks are related to improper administration and will be mitigated by safety procedures, such as the use of protective eyewear.

The risk of thermal injury from PBM administered with the parameters used in the studies we reviewed is considered minimal and limited to the skin. In ten people treated by TBI with 10-15 W lasers, a much higher power than that used in t-PBM, skin temperature increased to no more than 30°C with rapid cooling after removal of the NIR light. Clinically, patients reported slight skin heating, but no discomfort (Morries et al., 2015).

Near Infrared Transcranial Laser Therapy in Subjects with Major Depressive Disorder: A study of Dosing with Laser.

TITLE	PUBLISHED					NOT PUBLISHED			PRESENT
	NEST	NEST-2	NEST-3	ELATED	ELATED-2	ELATED-3	TRIADE	TRAP-AD	"ELATED-4"

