5.2 Aims of the Study

Primary Aims:

A. To compare the effect(s) of each of the four doses of NIR-TLT on depression symptomatology: antidepressant effect.

Hypothesis 1: Total HAM-D 17 scores will vary in a NIR-TLT dose-dependent manner, with BPW dose being more effective.

We also expect to be able to estimate the effect size of the antidepressant action as a function of the irradiance applied to the NIR-TLT skin, with the BPW dose being more effective.

B. Compare the safety and tolerability of each dose.

Hypothesis 2: The doses of NIR-TLT tested in this study will be safe and well tolerated by patients with MDD, as assessed by SAFTEE-SI and serious adverse events.

We do not anticipate dose-dependent differences in reported side effects.

Secondary Aims:

C. To compare the effect(s) of each of the four doses of NIR-TLT on brain electrophysiology.

D. To compare the effect(s) of each of the four doses of NIR-TLT on mitochondrial function.

Transcranial Near Infrared Laser Therapy in Subjects with Major Depressive Disorder: A Laser Dosing Study.

E. To study the correlations (correlating) antidepressant effects, brain electrophysiology and mitochondrial function of each of the NIR-TLT doses.

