5.3 Sample Size

The sample size was determined using G Power software version 3.1, considering a calculation by double mean difference with common standard deviation, assuming a significance level of 0.05 and 90% power. The parameters used were obtained from page 7 (section "Antidepressant effect according to clinician-rated measurement") of the previous ELATED-2 study (Cassano et al., 2018), where the mean difference of the HAM-D17 score for the experimental group was -10.8 ± 7.55 and for the control group 4.4 ± 6.65 ; such data identify a double difference of 6.4 with common standard deviation of 7.091. With this information, a total sample of 112 participants is obtained, taking into consideration a 20% loss rate. Each group will have 28 participants.

With $n=112$, in 4 groups in a longitudinal design, we estimated a power of 90% to differentiate ($\alpha=0.05$) the therapeutic effect of the dose, giving an antidepressant effect and an effect variance equivalent to that obtained in participants who completed the ELATED-2 study for all groups (Cassano et al., 2018b)

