In addition, the frequency and severity of side effects and adverse events reported for each dose will be compared using a Fisher's exact test. The corrective actions taken by the doctors as well as the clinical judgment on the likelihood of association of the side effect/adverse event with the NIR-TLT dose will also be reported.

D. Findings visualized in the PET scan:

The analysis of the results obtained in the PET will be for exploratory purposes to study the brain metabolism of the participants, before and at the end of the study intervention in the 4 groups. Following the recommendations of Daniel et al. (Daniel, 2012), for the exploratory analysis we will work with a minimum number of 5 participants per group, with a total of 20 participants.

The results obtained in the PET will be presented in a descriptive manner.

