5.6 Safety Analysis

The number and percentage of adverse events until the end of the study will be presented for each treatment group according to adverse event.

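### Hypothesis 2 expects no dose-dependent side effects, but the only between-arm inference fixed in 5.5 C is tests of difference, with no estimate or interval for the excess over sham

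*Protocol*

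**What the plan says.** Section 4.1 states the hypothesis as "Hypothesis 2: The doses of NIR-TLT tested in this study will be safe and well tolerated by patients with MDD, as assessed by SAFTEE-SI" together with serious adverse event reports. Sections 4.1 and 5.2 both add "We do not anticipate dose-dependent differences in reported side effects". The Summary and 4.1 rank this aim as secondary; 5.2 places it among the primary aims.

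Section 5.5 C gives two between-arm procedures:

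- A repeated-measures ANOVA on SAFTEE-SI at visits 1, 9 and 18, read by this rule: "A significant ANOVA interaction in mean score changes between groups will be taken as indicating that the NIR-TLT doses have different tolerability". Follow-up t-tests are run only if the interaction is significant.
- For events, "the frequency and severity of side effects and adverse events reported for each dose will be compared using a Fisher's exact test".

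Other safety outputs are planned. Section 5.5 C adds the corrective actions taken, and "the clinical judgment on the likelihood of association of the side effect/adverse event with the NIR-TLT dose will also be reported". Section 5.6 says "The number and percentage of adverse events until the end of the study will be presented for each treatment group according to adverse event". Section 5.7 adds descriptive statistics by arm. Sections 4.17.2 and 6.4.1 provide for DSMB review of serious adverse events.

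No margin, acceptable excess, between-arm confidence interval or safety power is stated. The sample size in 5.3 is set on HAM-D17, "assuming a significance level of 0.05 and 90% power".

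**The concern.** The result that Hypothesis 2 predicts is the absence of a difference. A test of difference can contradict that prediction but cannot establish it: a non-significant result may mean similar tolerability or too few participants. The protocol says what a significant interaction means and leaves the predicted result without a rule or an estimate to interpret.

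The descriptive tables show each arm's counts, but they do not give the excess over sham with its uncertainty. At 28 per arm, a non-significant comparison is a likely outcome even when one waveform is appreciably worse tolerated, and losing participants makes it likelier. In a study whose aim is to compare doses, the report should show how much excess harm the data leave open.

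**Working it through.** **Inputs from the protocol.** 28 per arm, four arms allocated 1:1:1:1, 20% loss, HAM-D17 difference 6.4 with SD 7.091 (4.4.1, 5.3). After loss, 28 × 0.8 = 22.4, so about 22 per arm. **Assumed**, because the protocol gives no value: the harm sizes, the within-person correlation (0.3, 0.5, 0.7, equal between all visits) and two-sided 0.05 for the safety tests.

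**1. The plan's own figure.** Standardised effect 6.4 / 7.091 = 0.90. The t-test sample size at 90% power with one-sided 0.05 is 22 per arm; 22 / 0.8 = 27.5, rounded up to 28; 28 × 4 = 112, which reproduces 5.3. (Two-sided 0.05 would give 27 per arm, 34 after loss and 136 in total.) So the number of participants was fixed by a 0.90 SD efficacy effect. Safety did not enter.

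**2. SAFTEE-SI interaction.** One arm is worse by 0, 0.5 and 0.5 SD at visits 1, 9 and 18. The F test has 6 and 2(4n − 4) degrees of freedom and noncentrality

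λ = n × (3/4) × Σ(profile − mean)² / (1 − ρ).

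The factor 3/4 is the sum of squared group deviations for one arm out of four; it is the same if all three active arms worsen equally. The profile sum is 1/9 + 1/36 + 1/36 = 1/6. Hence λ = 0.125 n / (1 − ρ).

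| n per arm | ρ | λ | Power | Missed |
|---|---|---|---|---|
| 28 | 0.3 | 5.00 | 33% | 67% |
| 28 | 0.5 | 7.00 | 46% | 54% |
| 28 | 0.7 | 11.67 | 71% | 29% |
| 22 | 0.3 | 3.93 | 26% | 74% |
| 22 | 0.5 | 5.50 | 36% | 64% |
| 22 | 0.7 | 9.17 | 58% | 42% |

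If the harm builds up instead (0.25 then 0.5 SD), at ρ = 0.5 the test misses 66% at 28 and 73% at 22. At 0.8 SD at both visits it misses 1–24% at 28 and 3–37% at 22 over the same correlations.

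**3. Participants with an event.** Power is the sum of binomial probabilities over all tables with Fisher p ≤ 0.05, one active arm against sham.

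| Rates | Missed, n = 28 | Missed, n = 22 |
|---|---|---|
| 10% v 30% | 67% | 72% |
| 20% v 40% | 72% | 79% |
| 10% v 50% | 11% | 21% |
| 5% v 15% | 92% | 91% |

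For a single four-arm Fisher test with one arm at 30% and the others at 10%, simulation gives about 50% missed at 28 and 62% at 22.

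**4. What an interval would show.** Take 9/28 (32%) in an active arm and 3/28 (11%) on sham. Fisher p = 0.10, not significant. The difference is 6/28 = 21 percentage points, and the 95% Newcombe interval runs from about 0 to 41 points.

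**5. Zero events.** The one-sided 95% upper limit for the rate is 1 − 0.05^(1/n): 10.1% for n = 28, and 3.5% for the 3 × 28 = 84 active participants together.

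**The case against.** Several stronger readings are tempting, and the document does not support them.

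- *A reader might infer that p > 0.05 will count as support for Hypothesis 2.* The protocol never says so. It attaches a meaning only to a significant interaction, and the sentence on dose dependence is an expectation, not a formal equivalence claim.
- *A reader might infer that safety is judged only by these tests.* It is not. Serious adverse event reports, arm-level tables, causality judgements and DSMB review all bear on whether the doses are safe. None of them, however, quantifies the excess over sham.
- *A reader might take a single miss rate as a property of the trial.* It is not one. With no stated event rate, SAFTEE-SI SD or relevant harm, the figure moves from about 1% to above 90% with the harm assumed.
- *A reader might cite section 4.3, "No significant differences in the rate of adverse effects were observed between the group receiving NIR laser" and sham, as the same error already made.* That is weak support: it concerns a combined sample of 1410, and the next paragraph of 4.3 reports more mild side effects on active treatment in another trial.
- *A reader might treat this as a primary aim.* Only 5.2 does so.

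Two further points carry some weight. Withdrawn participants still contribute events, because adverse events are recorded from consent and the exit visit includes the adverse event form and SAFTEE-SI where possible; the 22-per-arm Fisher figures are therefore pessimistic. Also, an analysis plan not shown here may add intervals. But the protocol itself fixes both the tests and the reading rule, and an analysis plan that followed it literally would inherit the gap.

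**Conclusion.** The point holds as an inexpensive improvement to a stated method. The inferential comparisons fixed for Hypothesis 2 can only detect differences, the trial was not sized for safety, and nothing planned in the protocol estimates the excess over sham with its uncertainty.

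Under an assumed 0.5 SD worsening on SAFTEE-SI, the interaction test misses 29–67% at 28 per arm and 42–74% at 22. Under an assumed 30% against 10%, the pairwise Fisher test misses 67–72%. These figures rest on two-sided 0.05, correlations of 0.3–0.7 and harm sizes that the protocol does not supply. The conclusion does not depend on any one of them: a non-significant result at this size is weak evidence of similar tolerability unless the interval is shown.

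**What to change.** In 5.5 C, keep both tests as supportive. For each active arm, and for the three active arms pooled, each against sham, report:

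- the difference in the proportion of participants with an event, with its two-sided 95% confidence interval;
- the difference in mean SAFTEE-SI change, with its 95% confidence interval.

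Add a sentence such as: *A non-significant test will not be taken as evidence of equal safety or tolerability; the conclusion will state the largest excess over sham that the upper confidence limit does not exclude.* For an event not seen at all, state the one-sided 95% limit on the rate: 10% in an arm of 28, 3.5% in 84 pooled.

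Rewording Hypothesis 2 in 4.1 and 5.2 as estimation of the excess over sham is optional.

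The cost is a few sentences and some intervals from data already collected, with no extra participants or procedures. The downside is wide intervals (up to 41 points in the example above) and a less favourable safety statement.
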